## Statistical Analysis Plan

1. Statistical Analysis Plan and Sample Size Justification	
* Statistical Analysis Plan
 
Statistical analyses will be performed using SPSS software (SPSS version 20.0, IBM, Chicago, IL, USA).
 
Student's t-test or Mann-Whitney U-test will be used to compare continuous data including the mean values of the peak inspiratory pressure, the pressure of back muscle retractor and recovery time between the groups. Though measurement timepoints of peak inspiratory pressure and pressure of back muscle retractor are multiple, the mean value of each timepoint will be calculated and the mean value of each group will be analysed by Student's t-test.
 
The normal distribution of the continuous data will be first evaluated using the Shapiro-Wilk test (<math>P > 0.05</math>). The normally distributed data will be analysed using the Student's t-test, and the abnormally distributed data will be analysed using the Mann-Whitney U-test.
 
Ordinal variables including, the degree of bleeding of each patient scaled by surgeons, assessed using a 6-point scale and overall satisfaction of surgeons, assessed using numerical rating scale (NRS; 1-10) will be compared using the Mann-Whitney U-test. Categorical variables such as the muscle tone of each patient scaled by surgeons, assessed using a 3-point scale, the number of body movements during the surgery and the incidence of adverse events between the groups will be compared using a chi-squared test (or Fisher's exact test).
 
The data will be expressed as the mean <math>\pm</math> standard deviation, median (25; 75 quartiles), or number of patients (%). P-values will be reported as two-tailed values and a P-value <math>< 0.05</math> will be considered statistically significant.
 
* Sample size calculation
 
Primary endpoint in this study is mean value of peak inspiratory pressure during the surgery. The sample size calculation was based on the results of a pilot study with 10 cases in each group. In the pilot study, peak inspiratory pressure (mean <math>\pm</math> standard deviation) was <math>18.8 \pm 2.9</math> cmH2O in Group DB and <math>20.7 \pm 3.0</math> cmH2O in Group RB, respectively. Therefore, the effect size of 2-groups was 0.64. On the assumption that the allocation ratio of 2-groups was 1, a sample size of 39 patients was selected for each group, calculated by Student's t-test, two-sided test, a level of significance of 0.05 and a power of 0.8. We estimated a 15% drop-out, resulting in the final enrolment of 45 patients in each group (total, 90 patients).

---	--

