# Study Protocol

Official Title : Comparison of Operating Conditions, Postoperative Recovery and Overall Satisfaction Between Deep and Restricted Neuromuscular Blockade for Spinal Surgery Under General Anesthesia

Identifiers : NCT02724111

Date of Document : 4th February 2016

Protocol of the Research	
1.1 Objectives & Hypotheses	
* Objectives
 
Primary Outcome Measure(s):
 
 
1. Mean Value of Peak Inspiratory Pressure [Time Frame: Every 15 minutes during anesthesia]
 
 
Secondary Outcome Measure(s):
 
 
2. Mean Value of Pressure of Back Muscle Retractor [Time Frame: Every 15 minutes during the placement of the retractor]
 
3. Overall Satisfaction of Surgeons for the Surgical Condition [Time Frame: After surgery]
 
4. The Muscle Tone [Time Frame: at the screw insertion through the pedicle of spine during surgery]
 
5. The Number of Body Movements [Time Frame: Throughout the surgery]
 
6. The Degree of Bleeding [Time Frame: Throughout the surgery]
 
7. Recovery Time (Time to Reach Sedation Score 5 at Post-anesthesia Care Unit (PACU). [Time Frame: every 10 min for 1 hour at PACU.]
 
8. Adverse Events [Time Frame: during the postoperative 24 hours]
 
 
* Clinical hypotheses
 
 
(1) Mean value of peak inspiratory pressure (PIP) is lower in deep NMB group than in restricted NMB group. The higher PIP in restricted NMB group is related to the more surgical bleeding compared to deep NMB group.
 
(2) Operating conditions including the number of body movement, degree of bleeding and muscle tone in deep NMB group are superior to restricted NMB group.
 
(3) Overall satisfaction of surgeons in deep NMB group is superior to restricted NMB group.
 

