	
· Ventilator settings: Tidal volume 8 mL/kg, respiratory rate initially 10 to 12 breaths/min, positive end-expiratory pressure (PEEP) 4 cmH2O and inspiratory-to-expiratory time ratio 1:2. Mechanical ventilation (respiratory rate) will be adjusted to maintain an end-tidal partial pressure of carbon dioxide at between 30 and 35 mmHg during surgery.
 
· Maintenance: The patients will be allocated to one of the 2 groups receiving either DEEP NMB (group DB) or RESTRICTED NMB (group RB) according to the assignment using a computer random number generator.
 
· NMB: In the group DB, rocuronium will be administered to maintain deep NMB (TOF count 0, PTC of 1-2 twitches) until the end of surgery and the reversal of NMB will be performed by sugammadex 4 mg/kg.
 
In the group RB, sugammadex will be administered according to the prescribing indications (4 mg/kg for deep NMB state or 2 mg/kg for moderate NMB or less) to reverse the NMB 10 min after position change (10 min after placing the patient prone). Thereafter, muscle relaxants will not be injected any more throughout the surgery except the following situations: If the patients show any body movement during surgery or if surgeons express any complaint about muscle tone (the muscle tone: grade 3), rescue rocuronium 5 mg will be administered and the number of body movements and rescue rocuronium administration (dose) will be recorded.

1.6 References	
 
Edmonds HL Jr, Paloheimo MP, Backman MH, Johnson JR, Holt RT, Shields CB. Transcranial magnetic motor evoked potentials (tcMMEP) for functional monitoring of motor pathways during scoliosis surgery. Spine (Phila Pa 1976) 1989;14(7):683-6.
 
 
Kalkman CJ, Drummond JC, Kennelly NA, Patel PM, Partridge BL. Intraoperative monitoring of tibialis anterior muscle motor evoked responses to transcranial electrical stimulation during partial neuromuscular blockade. Anesth

Analg 1992;75(4):584-9.

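### The number of body movements is recorded as a count per patient, but the SAP compares it by chi-squared or Fisher and does not say how counts become categories

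*SAP*

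**What the plan says.** Protocol section 1.1 lists as secondary outcome 5 "The Number of Body Movements [Time Frame: Throughout the surgery", with the whole operation as the time frame. Hypothesis (2) in the same section is directional and names this outcome first: "Operating conditions including the number of body movement, degree of bleeding and muscle tone in deep NMB group are superior to restricted NMB group".

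Protocol section 1.5 says what is collected when a patient moves or the surgeon complains of grade 3 muscle tone. Rescue rocuronium is given, and "the number of body movements and rescue rocuronium administration (dose) will be recorded". The recorded variable is therefore a count for each patient, not a yes/no item.

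SAP section 1 sorts outcomes into three types:
- Continuous data go to the t-test, or to Mann-Whitney if not normal.
- Outcomes it labels ordinal (bleeding on a 6-point scale, surgeon satisfaction from 1 to 10) go to Mann-Whitney.
- Outcomes it labels categorical go to chi-squared or Fisher. Here it says "the number of body movements during the surgery and the incidence of adverse events between the groups will be compared using a chi-squared test".

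The reporting formats include "median (25; 75 quartiles), or number of patients" with percentages, but no format is tied to a particular outcome. Neither document states a movement rate, or an effect size or power for this outcome.

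**The concern.** The outcome and the hypothesis are about how many times patients move. A chi-squared or Fisher test needs categories, and the SAP does not define them. Two codings fit its wording.

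- **Each count value is a category.** The test then treats 0, 1 and 4 movements as unrelated labels. A small p-value need not mean that either group moves less, and a real shift towards fewer movements is harder to detect.
- **Any movement versus none.** The test is valid for the proportion of patients who move, but it cannot see whether those who move do so once or several times.

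The two codings can give opposite answers on the same data. With the choice left open, it could be made after the data are seen.

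**Working it through.** **1. The plan's own figure.** The only sample-size calculation is for peak inspiratory pressure. From the pilot means and SDs, d = (20.7 − 18.8) / √((2.9² + 3.0²)/2) = 1.9 / 2.950 = 0.644, and the SAP states "the effect size of 2-groups was 0.64". With a "two-sided test, a level of significance of 0.05 and a power of 0.8", the normal approximation gives n = 2 × (1.960 + 0.842)² / 0.64² = 38.3, so 39 per group, as stated. This figure reproduces but says nothing about movements. It is used below only as the number of evaluable patients per arm.

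**2. Each value a category: order is ignored.** Take 45 patients per arm with 0/1/2 movements in 10/25/10 patients in one arm and 20/5/20 in the other.
- Mean counts: (25 + 20)/45 = 1.0 and (5 + 40)/45 = 1.0.
- Expected count in every cell: 15.
- Chi-squared = 2 × (25/15 + 100/15 + 25/15) = 20 on 2 degrees of freedom, p = exp(−10) = 0.00005.
- Mann-Whitney: p = 1.0.

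**3. Any versus none: frequency is ignored.** Take 20 of 45 patients moving once in one arm, and 20 of 45 moving four times in the other.
- Mean counts: 20/45 = 0.44 and 80/45 = 1.78.
- Any versus none: 20/45 against 20/45, p = 1.0.
- Mann-Whitney on the count: p = 0.07.
- Each value a category (25/20/0 against 25/0/20, expected 25/10/10): chi-squared = 2 × (100/10 + 100/10) = 40 on 2 degrees of freedom, p = exp(−20), about 2 × 10⁻⁹.

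So the undefined coding alone can take the same data from p = 1.0 to a very small p-value.

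**4. Power under assumed rates.** Inputs: 39 per arm, two-sided 0.05, over-dispersed counts (gamma-Poisson, shape 1.5), 2,000 to 4,000 simulated trials. Means and shape are assumptions.

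| Mean DB vs RB | Chi-squared, each value a category | Mann-Whitney on count | Uncorrected chi-squared, any vs none | Fisher, any vs none |
|---|---|---|---|---|
| 0.3 vs 0.9 | 49% | 78% | 71% | 62% |
| 0.1 vs 0.5 | 61% | 84% | 82% | 74% |

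Repeat runs moved these figures by about 1 to 3 points. The loss against Mann-Whitney is 78 − 49 = 29 and 84 − 61 = 23 points for the count table. For any versus none by uncorrected chi-squared it is 78 − 71 = 7 and 84 − 82 = 2 points.

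**5. Range over other assumed rates** (Poisson or negative binomial, 39 per arm).
- Each value a category: below Mann-Whitney in every scenario tried, by about 7 to 53 points.
- Any versus none, uncorrected chi-squared: within about 4 points of Mann-Whitney, or slightly above it, when the RB mean is 0.7 or less. It is about 12 to 48 points lower when the RB mean is 1 or more.
- Any versus none, Fisher: about 6 to 35 points lower at the low rates.

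**The case against.** The strongest reply is that the SAP means patients with any movement versus none. The outcome shares its sentence with the incidence of adverse events, and numbers of patients with percentages are among the reporting formats. On that reading the test is valid. If movements are rare, it gives up almost nothing against Mann-Whitney. Rescue rocuronium after a movement may also hold counts near 0 or 1, whereas the simulations let patients keep moving with no rescue effect. All of this stands, and it limits the size of the point. It does not remove it: the SAP does not state that coding, and the outcome and hypothesis name the number of movements.

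A reader might infer more than the documents support:
- **That the plan loses much of its power whatever is meant.** The loss depends on the coding and on movement rates that are not given.
- **That movements would be pooled across patients and treated as independent.** Nothing in the text suggests this.
- **That unequal operation lengths bias the comparison.** Allocation is randomised, so duration before treatment effects is balanced in expectation.
- **That any versus none is free of rescue effects.** A muscle-tone complaint also triggers rescue and could come before a first movement.

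**Conclusion.** The point holds in a limited form. The analysis stated for secondary outcome 5 does not match the outcome as defined and recorded, and the coding that would settle the matter is missing. If each count value is a category, the test ignores order and loses about 23 to 29 points of power in the two main scenarios. If any versus none is meant, the test is sound for a different question, with a loss of about 2 to 7 points by uncorrected chi-squared in the same scenarios and more when movements are frequent. All power figures rest on assumed rates and dispersion, and effective rescue would shrink them. The order and frequency examples in steps 2 and 3 need no assumed rates. This is an inexpensive improvement to one secondary outcome.

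**What to change.** In SAP section 1, define the outcome as the number of body movements per patient and compare it by Mann-Whitney, as the SAP already does for bleeding and satisfaction. Report separately the number of patients with at least one movement, by chi-squared or Fisher.

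A negative-binomial rate ratio with a 95% confidence interval and log duration of surgery as offset is an option only if duration is recorded. The documents do not say that it is, so this would have to be confirmed first. Mann-Whitney does not need it, although it gives no rate ratio and does not adjust for duration or rescue.

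The cost is a change of SAP wording and one extra line in the secondary results. Movement counts are already to be recorded, and no further patients are needed.

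### At 15% drop-out, 45 per group leaves 38.25 evaluable patients on average, short of the 39 set for 80% power; 45 covers 6 losses per group (13.3%).

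*SAP*

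**What the plan says.** The section of the SAP headed Sample size calculation builds enrolment in two steps.

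- **Evaluable number.** From a pilot with 10 cases per group, peak inspiratory pressure was 18.8 (SD 2.9) cmH2O in Group DB and 20.7 (SD 3.0) cmH2O in Group RB, and "the effect size of 2-groups was 0.64". With equal allocation, "a sample size of 39 patients was selected for each group", "calculated by Student's t-test, two-sided test", at "a level of significance of 0.05 and a power of 0.8".
- **Enrolled number.** "We estimated a 15% drop-out, resulting in the final enrolment of 45 patients in each group (total, 90 patients".

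Protocol sections 1.3 (inclusion criteria) and 1.4 (flowchart) carry the same totals: 90 patients, 45 per group. Neither document gives the formula that turns 39 into 45, or says whether the 15% is a share of those enrolled or of those analysed.

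**The concern.** Patients are lost from those enrolled, so a drop-out allowance is normally the required number divided by one minus the rate. That gives 46 here, not 45. The stated 45 is what results from adding 15% to the 39, or from dropping the decimals of 45.88.

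The 39 has almost no slack above 80% power, so any shortfall below 39 takes the design under its stated power. The allowance is also likely to be used. Protocol section 1.3 lists among its exclusions events that can arise only during surgery, such as blood loss above 1 L, so losses after enrolment are foreseeable. What is at stake is the accuracy of a power statement, not the validity of any analysis.

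**Working it through.** **Inputs, all from the SAP's sample size calculation:** pilot means 18.8 and 20.7, SDs 2.9 and 3.0, stated effect size 0.64, two-sided α = 0.05, power 0.80, allocation 1:1, 39 evaluable per group, 15% drop-out, 45 enrolled per group.

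**Step 1: reproduce the 39.**

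- Pooled SD = √((2.9² + 3.0²)/2) = 2.950.
- d = (20.7 − 18.8)/2.950 = 1.9/2.950 = 0.644.
- Power of the two-sample t-test comes from the non-central t distribution with df = n₁ + n₂ − 2 and non-centrality d·√(n₁n₂/(n₁ + n₂)). With 39 per group, df = 76, the non-centrality is 0.644 × √(39/2) = 2.84 and power is 0.802.
- Solving for power 0.80 gives n = 38.84, so 39. The plan's figure reproduces from the unrounded effect size. With d rounded to 0.64, the exact t-test asks for 40.

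**Step 2: reproduce the 45.**

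- 39 × (1 + 0.15) = 44.85, which rounds up to 45 and matches the plan.
- 39/(1 − 0.15) = 45.88, which rounds up to 46. Truncating it would also give 45.

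**Step 3: what 45 leaves after a 15% loss.**

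- Per group: 45 × 0.85 = 38.25, against 39.
- In total: 90 × 0.85 = 76.5, against 2 × 39 = 78.
- For comparison, 46 × 0.85 = 39.1.

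**Step 4: the loss that 45 does cover.**

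- 45 − 39 = 6 patients, and 6/45 = 13.3%.
- A seventh loss is 7/45 = 15.6% and leaves 38.
- Over both groups, 13 losses (13/90 = 14.4%) leave 77, for example 39 and 38.

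**Step 5: power (two-sided 0.05, exact t-test).**

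| Evaluable per group | How it arises | d = 0.644 | d = 0.64 |
|---|---|---|---|
| 39 and 39 | 6 of 45 lost in each group | 0.802 | 0.797 |
| 39 and 38 | 13 of 90 lost | 0.796 | 0.792 |
| 38.25 each | 15% lost on average | 0.794 | 0.789 |
| 38 and 38 | 7 of 45 lost in each group | 0.791 | 0.786 |

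With 46 enrolled and 15% lost (39.1 per group), power at d = 0.644 is 0.803.

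**The case against.** There are four arguments for leaving the sentence alone.

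1. **It can be read consistently.** Patients are whole. If 15% is a ceiling within each group, then 15% of 45 is 6.75, at most 6 can be lost, and 39 remain. Also, 39 × 1.15 gives 45, and the SAP never states its formula. This stands as an account of how 45 may have arisen. But the SAP says 15% was estimated, which reads as an expected rate rather than a ceiling, and the ceiling reading works only because the loss then stops at 13.3%.
2. **The gap is below the precision of the stated power.** The SAP gives power as 0.8, and every value in the table rounds to 0.8. This stands, and it is why the point is minor.
3. **Rounding the effect size matters as much.** Moving d from 0.644 to 0.64 changes the required number from 39 to 40, a shift as large as the gap itself. This stands and limits how exactly any corrected sentence can claim 80%. It does not rescue the sentence, because at 0.64 the power after 15% loss is lower still (0.789).
4. **The pilot is far less certain than this correction.** With 10 per group, SE(d) ≈ √(2/10 + 0.644²/40) = 0.459, so an approximate 95% interval is 0.644 ± 1.96 × 0.459, or −0.25 to 1.54. This also stands. True power is uncertain by much more than one point, but that does not make the drop-out step correct on the plan's own inputs.

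**Conclusion.** The point holds as a small arithmetic inconsistency. On the plan's own figures, 45 per group does not retain 39 at an expected 15% loss. It falls short by 0.75 patient per group, 1.5 in total. Power then is about 0.79, which is 0.6 of a percentage point below the stated 0.80 at d = 0.644 and 1.1 points below it at d = 0.64.

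The conclusion assumes that 15% is the expected proportion lost among enrolled patients, that lost patients contribute nothing to the primary analysis, and that the pilot effect size is taken at face value. Under the whole-patient ceiling reading the three figures can be reconciled, so the wording needs correcting and the design does not.

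**What to change.** Keep 90 patients and restate the SAP's drop-out sentence in one of two ways:

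- *Enrolling 45 per group allows for 6 losses per group (about 13%) while retaining the 39 per group needed for 80% power*; or
- *With 15% drop-out, about 38 patients per group would be evaluable and power would be about 0.79*.

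In either case, add that the 39 was derived from the unrounded effect size (0.644), since at 0.64 the power with 39 per group is 0.797.

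The cost is one sentence and a short clarification. No patients are added, the test and α are unchanged, and the stated figure becomes slightly less favourable. Raising enrolment to 46 per group (92 in total) would also make the figures agree, but it would mean changing the totals in Protocol sections 1.3 and 1.4 for about one point of power, so rewording is the more proportionate choice.
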